Treatment outcomes of full pulpotomy using two different calcium silicate-based materials in mature permanent teeth with irreversible pulpitis symptoms: A randomized clinical trial

NCT number: has not been created yet

Document Date;

Date of creation: 05.12.2023

Study Protocol

In this clinical study, patients will be blind; they will not know the material applied. The physicians performing the clinical and radiographic assessment will be blind; they will make the assessment without knowing which material it is. The person performing the statistical analysis will be blind to the groups. (Since the application procedures of the two materials to be applied are different, it is not possible to blind the physician performing the application.)

After the necessary clinical examination, the volunteers who meet the inclusion criteria for the study will be assigned to two separate groups by a physician outside the study according to the numbers created in the randomization table and recorded on the patient cards. The volunteers will be given standard oral hygiene training before the treatment. Two different calcium silicate-based materials (Biodentine or NeoPUTTY) will be applied as recommended by the manufacturers and specified in the user manual. All treatments will be performed by a single physician (endodontist) using dental magnification.

After the decay is cleaned and the exposed pulp is completely removed and calcium silicate cements of both groups will be placed on the remaining root pulp, all stages will be the same for both groups and stated below;

A periapical radiograph will be taken from the relevant tooth for diagnostic purposes before treatment. The radiograph will be taken with a parallel technique with the x-ray holder. The procedure will be performed by placing a small amount of silicone impression on the bite block

of the x-ray holder and taking an x-ray by biting the patient in order to ensure better quality of standardization. The same silicone impression will be disinfected and stored in the patient file under appropriate conditions and will be used in post-treatment and follow-up x-rays, and the radiographs to be taken will be at the same angle (after the filling is made, the filled part of the tooth will be abraded in the silicone for the silicone impression to fit). In addition, high-quality images will be taken from the relevant teeth with a camera before, during and after treatment. Deep local anesthesia will be provided in the tooth and surrounding tissues using lidocaine anesthesia with epinephrine. A rubber dam will be placed on the involved tooth and the oral environment will be isolated. After the tooth has been cleaned with chlorhexidine, initial caries removal will be performed circumferentially using a sterile high-speed diamond bur. Deeper layers of caries will be removed using a series of sterile low-speed burs of different diameters. Once the pulp tissue has been exposed by complete caries removal, initial total removal of the pulp tissue will be performed using a new sterile high-speed bur. After examination of the area for residual caries, the cavity will be irrigated with 5.25% NaOCl to remove carious dentine shavings and to initially disinfect the tissue and cavity. To control bleeding, a moist cotton pellet impregnated with NaOCl will be placed on the pulp wound surface for 2 minutes. If bleeding persists after removal of the cotton pellet, a new sterile cotton pellet soaked in 5.25% NaOCl solution will be placed on the pulp for a further 2 minutes. The bleeding will be checked every 2 minutes until the 10th minute, and pulp capping will be performed when the bleeding stops at any of these control intervals. If bleeding continues for more than 10 minutes, the case is deemed unsuitable and root canal treatment will be applied. After hemostasis is achieved, pulp capping material (Biodentine or NeoPUTTY) will be placed (Detailed explanations of these sections are provided below). Then, permanent composite material fillings will be made, filling photographs will be taken and periapical radiographs will be taken with silicone impressions. Routine post-treatment recommendations and post-operative pain information will be given to the patient and they will be asked to fill in the post-operative pain scale up to the 1st week after treatment and note the medications and doses if used. The patient will be checked at the 1st week (only for pain assessment) and at the 3rd, 6th and 12th months. During the controls, the necessary clinical examination (percussion, palpation, presence or absence of sinus tract) will be performed, vitalometric examination will be recorded, lamina dura will be radiated with silicone impression, lesion presence and canal obliteration will be evaluated and filling quality scoring will be performed. If conditions such as pain, swelling, sinus tract formation or lesion development are detected during the follow-up process, the patient will undergo root canal

treatment and will be evaluated as an unsuccessful case. Radiographic follow-up evaluations of the patients will be performed by two endodontic specialists independent of the study.

Biodentine group: After mixing the Biodentine material according to the instructions in the application guide, it will be placed on the pulp with hemostasis with the help of the carrier and condensed vertically so that no visible pulp tissue remains. After waiting for a setting period of 12 minutes, a self-etch bond will be applied around it, thinned with air and then cured. After the flowable composite is placed on the Biodentine material, it will be cured. Then, selective acidification will be applied to the enamel in the cavity, after it is removed with water and dried, self-etch bond will be applied to the cavity and irradiated and composite filling will be applied in layers. If possible, fillings will also be performed under rubber dam. If there is a problem in the matrix placement processes with rubber dam, Biodentine will be completely covered with flowable composite and after irradiation, the rubber dam will be removed and filling will be continued.

NeoPUTTY group: NeoPUTTY material will be placed on the pulp with hemostasis with the help of the carrier with a thickness of at least 1.5 mm so that no visible pulp tissue remains. Then, a self-etch bond will be applied around it and thinned with air and then cured. NeoPUTTY will be cured after the flowable composite is placed on it. The remaining procedures are the same as the Biodentine group.

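### The arm is assigned before the intra-operative bleeding test, and nothing keeps it from the single operator until haemostasis

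*Protocol*

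**What the plan says.** All places are in the Protocol under the heading Study Protocol.

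- **Assignment paragraph.** The clinical examination comes first; then "the volunteers who meet the inclusion criteria for the study will be assigned to two separate groups by a physician outside the study". The method and the record of assignment are given as "according to the numbers created in the randomization table and recorded on the patient cards". Oral hygiene training before treatment is mentioned next.
- **Same paragraph, operator.** "All treatments will be performed by a single physician (endodontist) using dental magnification".
- **Blinding paragraph.** Patients, clinical and radiographic assessors and the analyst are blinded. The operator is not: "Since the application procedures of the two materials to be applied are different, it is not possible to blind the physician performing the application".
- **Operative steps, bleeding control.** Bleeding is checked every 2 minutes up to 10 minutes, and "pulp capping will be performed when the bleeding stops at any of these control intervals". Otherwise: "If bleeding continues for more than 10 minutes, the case is deemed unsuitable and root canal treatment will be applied".
- **Operative steps, placement.** "After hemostasis is achieved, pulp capping material (Biodentine or NeoPUTTY) will be placed".
- **Biodentine group paragraph.** "After mixing the Biodentine material according to the instructions in the application guide, it will be placed on the pulp with hemostasis". The NeoPUTTY group paragraph likewise starts with placement on pulp in which bleeding has stopped.

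**The concern.** Eligibility is in effect completed after assignment. A tooth can be assigned to an arm, fail the bleeding test, and leave without receiving either material. One person decides this, by looking at whether bleeding has stopped, and the protocol makes no provision to keep that person unaware of the arm.

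If the operator knows the arm and judges borderline bleeding differently by arm, exclusion depends on the arm. The teeth that remain are then no longer a randomised comparison. If the operator does not know the arm, or judges both arms alike, that bias does not arise. What is left is a set of assigned teeth that received no study material, and this document does not say how they are counted. Both problems follow from when the allocation is made and released, and both can be avoided.

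**Working it through.** **Order of steps.** The protocol gives no figure to reproduce, so the check begins with the sequence as written:

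1. Clinical examination.
2. Assignment from the randomisation table by the outside physician, with an entry on the patient card.
3. Hygiene training, anaesthesia, rubber dam, caries removal and pulp removal, all common to both arms.
4. Bleeding control, with checks every 2 minutes to a limit of 10 minutes. Teeth that fail leave for root canal treatment.
5. Placement of Biodentine or NeoPUTTY.

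Assignment is at step 2, exclusion at step 4, and the first arm-specific placement at step 5. The only arm-specific act that could begin before step 5 is mixing Biodentine, and the text does not say when mixing starts. The reason given for not blinding the operator therefore does not extend to step 4, unless mixing is begun during the checks.

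Two points stay open. The grammar does not settle whether the card shows the arm or only a randomisation number. Nor does the text say who holds the card before placement.

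**Scale, with every input assumed.** The document gives no bleeding rate and no failure rate. Take two identical materials and leave excluded teeth out of the comparison.

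- b = share of opened teeth with borderline bleeding, 0.05 to 0.20
- fb = failure risk in borderline teeth, 0.20 to 0.40
- fo = failure risk in the other teeth, 0.08
- d = share of borderline teeth excluded in an arm

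The failure risk among the teeth kept in an arm is

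f(d) = [b(1 − d)fb + (1 − b)fo] / [b(1 − d) + (1 − b)]

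The spurious difference is f in the arm with less exclusion minus f in the arm with more.

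At b = 0.10 and fb = 0.30:

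| Excluded, arm A vs B | f, arm A | f, arm B | Difference (points) |
|---|---|---|---|
| 50% vs 50% | (0.0150 + 0.072)/0.950 = 9.16% | 9.16% | 0 |
| 55% vs 45% | (0.0135 + 0.072)/0.945 = 9.05% | (0.0165 + 0.072)/0.955 = 9.27% | 0.22 |
| 60% vs 40% | (0.0120 + 0.072)/0.940 = 8.94% | (0.0180 + 0.072)/0.960 = 9.38% | 0.44 |

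At the ends of the assumed range:

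| b, fb | 55% vs 45% | 60% vs 40% |
|---|---|---|
| 0.05, 0.20 | 8.34% − 8.28% = 0.06 | 8.37% − 8.25% = 0.12 |
| 0.20, 0.40 | 11.87% − 11.24% = 0.63 | 12.17% − 10.91% = 1.26 |

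**Replacement if the allocation is released after haemostasis.** If a share e of opened teeth does not reach haemostasis, 100/(1 − e) teeth must be opened per 100 randomised. That is 105.3, 111.1 and 125.0 for e = 0.05, 0.10 and 0.20 (assumed).

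**The case against.** The bias route is inferred from silence. The protocol does not say that the operator sees the arm before placement, and an outside physician makes the assignment. The bleeding rule is timed, has a fixed limit and is the same in both arms, and nothing in the text gives the operator a reason to favour either material. The scale calculation depends wholly on assumed unequal exclusion, and on leaving excluded teeth out of the analysis, which an SAP might not do. It implies 2% (0.05 × 0.40) to 12% (0.20 × 0.60) of teeth excluded, so the 20% replacement case goes beyond it. Finally, releasing the allocation after haemostasis could delay placement in the Biodentine arm alone, since only that material is described as being mixed.

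Most of this stands as a limit on size and certainty. The effect is conditional, probably small and possibly zero, and the figures are illustrations only. The pre-treatment timing of assignment is also the natural reading rather than an explicit statement, and the inclusion criteria are not listed in the text at hand.

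The objection does not remove the point. The outside physician protects enrolment, not a later exclusion by the operator. The timed rule still needs a visual judgement at each check. An SAP can define which teeth are analysed, but it cannot change when the arm becomes known at the chairside.

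**Conclusion.** The point holds as a design weakness that is cheap to correct. On the natural reading, assignment precedes an intra-operative exclusion decided by one operator, no provision conceals the arm until that decision is made, and the stated obstacle to blinding begins only with material handling.

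No bias is shown. Under the assumptions above, the spurious difference is 0 with equal exclusion and at most 1.26 percentage points at the extreme of the range. Confidence is moderate, because the operator's knowledge of the arm is neither stated nor ruled out. The case for acting is the low cost of the change, together with the removal of assigned teeth that received neither material.

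**What to change.** Move the release of the allocation and leave the bleeding rule as it is. Suggested text:

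> After haemostasis is confirmed under the rule below, the physician outside the study releases the next allocation (sealed opaque envelope or call), and the group is then entered on the patient card. Teeth that do not reach haemostasis are logged as screened, not randomised.

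**Cost.**
- A wording change and a chairside step. Both materials and the envelope or call must be available at every procedure.
- Biodentine can be mixed only after release, which adds time in that arm if mixing now starts during the checks. The sponsor should state when mixing starts and judge whether this matters.
- Teeth that do not reach haemostasis must be replaced: about 105, 111 or 125 opened per 100 randomised if 5%, 10% or 20% do not reach it.

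**Lighter alternative.** Keep the early assignment, have the outside physician hold the code until haemostasis, and report excluded teeth by arm. This closes the route to arm-dependent exclusion, but it still leaves assigned teeth that received neither material, and their handling in the analysis would have to be stated.

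### Is the declared assessor blinding undone by the patient card, the treatment photographs or the follow-up films?

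*Protocol*

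**What the plan says.** All of this is in the Protocol, under Study Protocol.

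- **Blinding paragraph.** Patients, assessors and the person analysing the data are declared blind. For assessors: "The physicians performing the clinical and radiographic assessment will be blind; they will make the assessment without knowing which material it is". For the operator, the paragraph concedes that "it is not possible to blind the physician performing the application".
- **Assignment paragraph.** Someone without a part in the trial allocates the volunteers, and this is done "according to the numbers created in the randomization table and recorded on the patient cards". One endodontist does all the treating: "All treatments will be performed by a single physician (endodontist) using dental magnification".
- **Procedure and follow-up text.** For records, "high-quality images will be taken from the relevant teeth with a camera before, during and after treatment". Periapical films are taken after the filling and at follow-up. The silicone bite impression is kept in the patient file for reuse. At the 3, 6 and 12 month controls there is a clinical examination, a radiographic evaluation and a filling quality score. Pain, swelling, a sinus tract or a lesion, given as examples, lead to root canal treatment and classification as a failure. Immediately after this: "Radiographic follow-up evaluations of the patients will be performed by two endodontic specialists independent of the study".
- **Material paragraphs.** NeoPUTTY is placed "with a thickness of at least 1.5 mm so that no visible pulp tissue remains". Biodentine is condensed vertically to the same end point, with no thickness given.

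**The concern.** With the operator unblinded, the comparison depends on the assessors' blinding to guard against detection bias. The Protocol asserts that blinding without saying how it is kept, and three features could defeat it:

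1. If the card carries the group and is to hand at the controls, the examiner can read the arm from it.
2. Photographs taken during treatment could show which material was used.
3. Follow-up films show the treated tooth with the cement in place, and the placement instructions differ between arms.

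Lesion presence is a matter of judgement and is one of the listed grounds for failure. Percussion, palpation, lamina dura and filling quality are also judged at these visits. An assessor who knew the arm and leaned one way could shift the apparent success rate of one material.

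**Working it through.** The Protocol states no figure that bears on blinding, so there is nothing to reproduce. The check is a reading of the text, followed by a calculation of what a leak could do.

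**Card.** In "according to the numbers created in the randomization table and recorded on the patient cards" the nearest thing that can be recorded is the numbers. On that reading the card holds a randomization number, which is normal practice. The other reading, that the group is recorded, is possible but not compelled. A bare number would still reveal the arm to someone holding the table, but the table is used by a physician outside the study and no passage gives it to an assessor. The text does not say that the card is used at the 3, 6 and 12 month controls. It mentions only a patient file holding the impression, and does not say that the card is in it.

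**Photographs.** They are to be taken. No passage says that they go to the assessors.

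**Films.** Seeing a cement reveals the arm only if the two cements look different. The Protocol gives no radiopacity or appearance for either. The thickness wording does not separate them: a minimum of 1.5 mm in one arm and no stated value in the other allow complete overlap. Both materials are placed until no pulp is visible, and both are covered with flowable and then layered composite.

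**Who assesses.** Film reading belongs to two specialists from outside the study. The clinical examiner is not named. However, the clinical assessors are declared blind and the operator is declared unable to be blind. Taken together, these exclude the operator from the clinical assessment.

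**Size if a leak did occur.** Assumed inputs, none from the Protocol: true failure *f* = 0.10 in both arms, and a proportion *e* of sound teeth wrongly called failures in one arm only. Apparent failure in that arm = *f* + (1 − *f*)*e*.

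| *e* | Apparent failure | Spurious difference |
|---|---|---|
| 0.02 | 0.10 + 0.90 × 0.02 = 0.118 | 1.8 points |
| 0.05 | 0.10 + 0.90 × 0.05 = 0.145 | 4.5 points |
| 0.10 | 0.10 + 0.90 × 0.10 = 0.190 | 9.0 points |

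The difference is (1 − *f*)*e*. If the same *e* applied in both arms it would be zero. The table therefore shows what one-sided over-calling would do in any such trial. It is not evidence that this plan permits it.

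**The case for a change.** The strongest reply is that a blinding procedure should not need charitable reading. Card contents, film coding and the identity of the examiner are matters of conduct, to be settled before the first patient, and they are not left to an analysis plan. The independent readers protect only the films. Percussion, palpation, sinus tract and vitality findings come from an examiner who is never identified, and the only treating clinician described is the unblinded one. The safeguards would also be cheap.

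Part of this stands. The Protocol does not say whether the card carries a number or the group, who sees the card and photographs, how films are coded, or expressly that the clinical examiner is someone other than the operator. The last is the most noticeable silence. But each is a detail left unsaid. No passage directs anyone to act against the blinding declaration, and the natural way to carry out that declaration closes each route: a number on the card, the table kept with the outside physician, films read without the operative record, and a blinded physician at the clinical examination.

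Routine masking of the crown has a weaker case. Filling quality is scored at the same controls, and the cement lies on the remaining root pulp, next to the canal where obliteration is read, so cropping might not hide it cleanly. Whether masking would gain anything depends on a difference in appearance that the Protocol does not show.

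**Conclusion.** The concern does not call for a change. The Protocol commits to blind clinical and radiographic assessment, places film reading with two specialists independent of the study, and has assignment done from outside. A team following it as written would have blind assessors. What is absent is the description of how, which is worth a clarifying question to the sponsor but is not an error or a contradiction.

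The 1.8 to 9.0 point range is arithmetically right, but it rests wholly on an assumed 10% failure rate and assumed over-calling in one arm only. The conclusion itself rests on two readings: that the card sentence does not require the group to be written down, and that the declaration about clinical assessors excludes the operator. It would change if the card were found to name the material in the assessors' sight, if the operator carried out the follow-up examinations, or if the cements proved distinguishable on film.

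### Could an apical lesion already present before treatment be counted as a failure, because the independent readers are assigned only the follow-up evaluations?

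*Protocol*

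**What the plan says.** All the relevant text is in the Protocol under Study Protocol.

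- **Failure rule** (end of the common treatment and follow-up description): "If conditions such as pain, swelling, sinus tract formation or lesion development are detected during the follow-up process", the patient goes to root canal treatment, "treatment and will be evaluated as an unsuccessful case".
- **Items at the control visits** (3, 6 and 12 months; the 1-week visit is for pain only): the list includes "lesion presence and canal obliteration will be evaluated and filling quality scoring will be performed".
- **Readers**: "Radiographic follow-up evaluations of the patients will be performed by two endodontic specialists independent of the study". The opening paragraph adds that those making the clinical and radiographic assessments do not know the material.
- **Pre-treatment film**: "A periapical radiograph will be taken from the relevant tooth for diagnostic purposes before treatment". The patient bites into a silicone impression on the film holder. That impression is stored and "will be used in post-treatment and follow-up x-rays, and the radiographs to be taken will be at the same angle". A further film is taken after the filling.
- **Eligibility**: inclusion criteria are mentioned but not listed.

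**The concern.** The failure criterion is a change (a lesion develops), while the visit item is a state (a lesion is present). A state read on one follow-up film cannot show whether the lesion is new. The independent readers are assigned the follow-up evaluations, and the only stated use of the pre-treatment film is diagnostic. On a literal reading, nobody blinded and independent scores the baseline, so the change could not be derived from independently read data.

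In teeth with symptoms of irreversible pulpitis, some apical change might already be visible at entry. If such teeth were scored on presence alone, they would be failures from the first film onward, even if stable or improving. Failure rates would then be inflated in both arms, the difference between materials diluted, and power lost. By chance, such teeth could also fall unevenly between the arms.

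**Working it through.** The document gives no success rate, sample size, power or prevalence of apical change, so there is no figure of its own to reproduce. The check has two parts.

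**1. The text, side by side**

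| Question | What the protocol states | What it leaves open |
|---|---|---|
| What is a radiographic failure? | A lesion that develops and is detected during follow-up | How development is judged from the visit records |
| What is recorded at each visit? | Whether a lesion is present | The scale, and any comparison rule |
| Who evaluates follow-up? | Two independent endodontic specialists | Which films they have in front of them |
| Are the films comparable? | Yes: same silicone index, same angle, before and after treatment and at follow-up | Nothing |
| Can teeth with apical change enter? | Not shown | Everything |

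Three things follow.

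- The reader sentence does not say that only follow-up films are viewed. That restriction would have to be added by whoever reads it.
- A lesion present at entry and unchanged has not developed during follow-up. To count it as a failure is to depart from the stated rule.
- Storing the index from the pre-treatment film and reusing it mainly serves comparison with that film. Recording a state at each visit and judging change across visits is ordinary practice and contains no contradiction.

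Canal obliteration and lamina dura are evaluated but are not among the named failure conditions. A canal that was narrow at entry is therefore not shown to become a failure.

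**2. Size if the miscount did happen**

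Assumptions, none from the document: true success of 95% and 85%; a share g of teeth in each arm has an apical change at entry, and every one of these persists, is read as a lesion and is counted as a failure.

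Observed success: p′ = p(1 − g).

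Required sample size is proportional to [p₁′(1 − p₁′) + p₂′(1 − p₂′)] / (p₁′ − p₂′)².

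Base case, g = 0: (0.0475 + 0.1275) / 0.10² = 0.175 / 0.01 = 17.5.

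| g | Observed success | Difference | Sum of variances | Sum / difference² | Ratio to 17.5 |
|---|---|---|---|---|---|
| 0% | 95% vs 85% | 10.0 points | 0.1750 | 17.50 | 1.00 |
| 2% | 93.1% vs 83.3% | 9.8 points | 0.20335 | 21.17 | 1.21 |
| 5% | 90.25% vs 80.75% | 9.5 points | 0.24344 | 26.97 | 1.54 |
| 10% | 85.5% vs 76.5% | 9.0 points | 0.30375 | 37.50 | 2.14 |
| 20% | 76.0% vs 68.0% | 8.0 points | 0.4000 | 62.50 | 3.57 |

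In terms of absolute failure, observed failure = f + g(1 − f). With an assumed f of 10%, this is 11.8% at g = 2%, 14.5% at g = 5% and 19.0% at g = 10%.

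The factor (1 − g) is the same in both arms in expectation, because assignment is random and the apical change precedes it. Equal true rates stay equal, so a test of difference is not tilted towards either material. The cost would be power and inflated absolute failure.

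**The case for a change.** The strongest case for a change is that reading a film is trial conduct. If nobody scores the pre-treatment film, no later analysis plan can derive a change from a score that was never recorded. A reader who sees a follow-up film and an item asking whether a lesion is present cannot separate new from old, however the failure rule is worded. Exclusion of apical change at entry would rest on the diagnostic reading, with which the two readers might not agree. The remedy would also be cheap: the films exist, the readers are engaged, and a film taken before any material is placed cannot reveal the arm.

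Part of this stands. The protocol nowhere assigns the readers a baseline score and nowhere says how presence is turned into development. The loss of power would also not be trivial if the miscount occurred, because variance rises while the difference shrinks.

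The step from there to a wrong result does not stand. It needs readers who are denied, or ignore, a matched film that the protocol takes care to produce, and who then apply a rule other than the stated one. It also needs eligible teeth with apical change, which the document neither confirms nor rules out. The pre-treatment films are taken in any case, so the comparison remains possible. Scoring scales and baseline comparison rules are commonly set out in an SAP, which may exist here.

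**Conclusion.** No change to the plan follows. What remains is missing detail: the link between the visit item and the failure criterion is not spelled out. The failure wording and the same-angle films both lead a sensible reader to judge development against the pre-treatment film, and following the protocol as written is not shown to misclassify any tooth.

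The size of the effect is unknown and may be zero. It is nil if apical change is excluded at entry, and nil if the failure rule is applied as worded. The sample-size ratios of 1.21 to 3.57 rest on assumed success rates, on an assumed 2% to 20% of teeth with apical change at entry, and on every such tooth being counted against the stated rule. The upper end combines the extremes of these assumptions. Even then, the expected consequence is dilution in both arms and not an advantage for one material.
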